At the next stage, the efficacy and safety of the double doses of Fortelyzin® (0.8 mg), Actilyse® (8.0 mg), and Purolase® (4.0 mg) in thrombolysis in rabbits with ischemic stroke were evaluated. The double doses studied correspond to 20 mg of Fortelyzin®, 200 mg of Actilyse®, and 16 mln/IU of Purolase® in humans.

Evaluation of the efficacy of double doses of the studied drugs in AIS rabbits has shown that such doses do not increase the area of lysis of the embolus, decrease the volume of brain infarction and reduce the amount of neurological damage according to the modified Bederson scale (MBS).

However, the double doses of Actilyse® and Purolase® led to a catastrophic drop in blood fibrinogen of more than 90%, causing the massive cerebral hemorrhages and death of animals.

The data obtained correspond to the literature data on the application of immunogenic staphylokinase in rabbits with ischemic stroke in comparison with Actilyse® (S. Vanderschueren, et al. Intravenous Thrombolysis With Recombinant Staphylokinase Versus tissue-type Plasminogen Activator in a Rabbit Embolic Stroke Model. *Stroke*. 1997; 28:1783-1788).

Therefore, the study of the two doses of Fortelyzin® - 0.4 mg and 0.8 mg - in rabbits with ischemic stroke, corresponding to 10 mg and 20 mg of Fortelyzin® in humans, showed their equal effectiveness and greater safety of a dose of 0.4 mg.

In connection with the above, a 10 mg dose of Fortelyzin® was selected for the treatment of patients with ischemic stroke.

First, such choice is due to the fact that the dose of 10 mg equivalent to 0.4 mg of Fortelyzin® in AIS rabbits has shown its high safety and comparable effectiveness with the doses of Actilyse® (4 mg) and Purolase (2 mg) used in ischemic stroke.

Secondly, the 10 mg dose of Fortelyzin® has also shown high efficacy and safety in the clinical trials (phase I and II) (page 18 of this protocol) of Fortelyzin® in comparison with Actilyse® (100 mg) in AMI patients.

Indications

- Ischemic stroke in men and women aged 18 and older
- After 80 years with caution
- The time from the onset of stroke symptoms is less than 4.5 hours.

Contraindications

Cerebral

1. Neuroimaging (CT, MRI) signs of intracranial hemorrhage, brain tumors
2. Hemorrhagic stroke or stroke of an unspecified nature in the anamnesis
3. Rapid improvement or mild symptoms by the time of the beginning of TLT

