4. Signs of a severe stroke: clinical [score on the National Institutes of Health Stroke Scale (NIHSS) > 25], neuroimaging (based on CT of the brain and/or MRI of the brain in the diffusion-weighted imaging (DWI) mode, the focus of ischemia extends to the territory of more than 1/3 of the CMA pool)
5. Seizures in the onset of the disease, if there is no certainty that the seizure is a clinical manifestation of ischemic stroke with a postictal residual deficiency
6. Previous stroke or severe traumatic brain injury within 3 months
7. Stroke of any genesis in the history combined with diabetes mellitus
8. Suspected subarachnoid hemorrhage (SAH)
9. Surgical intervention on the brain or spinal cord in the anamnesis

Cerebral and somatic

10. Arterial aneurysms, defects in the development of arteries or veins
11. Tumors with a high risk of bleeding

Somatic

12. Hypersensitivity to any component of the drug
13. Hemorrhagic diathesis

14. Arterial hypertension greater than 185/105 mm Hg or the need for intensive reduction below these figures
15. Bacterial endocarditis, pericarditis
16. Gastrointestinal bleeding or bleeding from the genitourinary system in the last 3 weeks. Confirmed exacerbations of gastric ulcer and duodenal ulcer during the last 3 months.
17. Liver failure (cirrhosis, active hepatitis, portal hypertension)
18. Acute pancreatitis
19. Present bleeding or extensive bleeding in the last 6 months
20. Extensive surgery, trauma, delivery, puncture of non-compressible vessels, cardiopulmonary resuscitation within the last 10 days
21. Pregnancy. Before the study, women of childbearing age will be asked to have a urine pregnancy test (determination of chorionic gonadotropin (HCG) in the urine).
22. Data on bleeding or acute injury at the time of examination.

Laboratory

23. Administration of warfarin and INR > 1,3
24. Use of heparin for 48 hours with increased aPTT
25. Thrombocytopenia less than 100,000/ μ l
26. Glycemia less than 2.8 and more than 22.5 mmol/l

Posology and method of administration

For Intravenous Use Only!

Fortelyzin® is administered intravenously as early as possible from the onset of clinical symptoms, but no later than 4.5 hours from its onset. The content of each of the two vials of 5 mg (745,000 IU) is diluted in 5 ml of isotonic sodium chloride solution. Fortelyzin® administered intravenously as a bolus dose of 10 mg for 5-10 s. The solution should be prepared immediately before use and should not be stored.

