3. POTENTIAL BENEFITS AND RISKS TO PARTICIPANTS

The expected benefit of using the drug is to restore normal blood circulation in the ischemic areas of the brain, which will normalize brain functions and avoid further disability of patients.

The possible undesirable effects of Fortelyzin® is the likelihood of bleeding. Local bleeding (injection sites, oral cavity), as a rule, does not require additional treatment.

Internal bleeding may be caused by latent forms of peptic ulcer, esophageal erosion, bleeding from hemorrhoidal veins, esophageal veins, etc. Thus, careful history taking with special attention to the above-mentioned diseases and a clear selection of patients taking into account all contraindications allows, in most cases, to minimize the risk of bleeding.

During thrombolytic therapy in patients with ischemic stroke, hemorrhagic transformation of the focus is possible. However, it is believed that the benefit of using drugs of this group in patients with thrombosis significantly exceeds the risk of bleeding.

During the study, all adverse events will be carefully controlled. If they appear, all available data will be evaluated and appropriate measures will be taken by the staff of the research centers.

All participants in this clinical study are insured. If a patient is harmed in the trial and this harm is a direct result of the action of the study drug and/or medical manipulations used in accordance with the Study Protocol, the Insurance Company undertakes to fully reimburse the participant all expenses for the necessary medical care.

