7.2. Exclusion criteria

- The time of the onset of the first symptoms is more than 4.5 hours from the onset of the disease or the time of the onset of the first symptoms of a stroke is not known (for example, the development of a stroke during sleep - the so-called "night stroke").

- Increased sensitivity to alteplase, gentamicin (residual traces from the production process).
- Systolic blood pressure greater than 185 mm Hg or diastolic blood pressure greater than 110 mm Hg or the need for intravenous administration of drugs to reduce the blood pressure to these boundaries.
- Neuroimaging (CT, MRI) signs of intracranial hemorrhage, brain tumors, arteriovenous malformation, brain abscess, aneurysm of cerebral vessels.
- Surgery on the brain or spinal cord.
- Suspicion of subarachnoid hemorrhage.
- Signs of severe stroke: clinical signs (stroke scale NIH > 25), neuroimaging (according to CT of the brain and/or MRI of the brain in the DWI, the ischemia focuses on the territory of more than 1/3 of the MA pool).
- Simultaneous administration of oral anticoagulants, for example, warfarin with INR > 1.3.
- The use of direct anticoagulants (heparin, heparinoids) in the 48 hours preceding the stroke with APTT values above the norm.
- Prior stroke or severe head injury within 3 months.
- Significant regression of neurological symptoms during the observation of the patient
- Light neurological symptoms (NIH < 4 points)
- Hemorrhagic stroke or stroke, unspecified in history.
- Strokes of any genesis in the history of a patient with diabetes mellitus.
- Gastrointestinal bleeding or bleeding from the genitourinary system in the last 3 weeks. Confirmed exacerbations of gastric ulcer and duodenal ulcer during the last 3 months.
- Extensive bleeding, present or within the previous 6 months.

- Severe liver disease, including liver failure, cirrhosis, portal hypertension (with varicose veins of the esophagus), active hepatitis.
- Acute pancreatitis.
- Bacterial endocarditis, pericarditis.
- Aneurysms of arteries, malformations of arteries and veins. Suspicion of exfoliating aortic aneurysm.
- Neoplasms with an increased risk of bleeding.
- Large operations or severe injuries within the last 14 days, minor surgery or invasive manipulation in the last 10 days.
- Puncture of uncompensated arteries and veins during the last 7 days.
- Prolonged or traumatic cardiopulmonary resuscitation (more than 2 min).
- Pregnancy, obstetrics, 10 days after delivery.

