9. TRIAL PROCEDURES

Visit 1 (Start of the trial)

Prior to administration of the trial drug, all patients will undergo the following procedures:

- determination of inclusion/non-inclusion criteria
- signing of Informed consent
- collection of demographic data (date of birth, sex)
- collection of medical history (duration of the underlying disease, previous therapy, allergological anamnesis, etc.)
- physical examination
- evaluation of changes by organs and systems
- assessment of neurological status using the NIHSS and modified Rankin scales (mRS)
- Duplex scanning of the major arteries of the head (if necessary)
- CT/MRI examination of the brain
- assessment of CT changes according to ASPECTS (Alberta Stroke Program Early CT Score)
- angiography of the cerebral vessels (if necessary)
- blood sampling for hematological and biochemical analyses
- coagulogram
- common urine analysis
- ECG
- assessment of the patient's compliance with the inclusion/exclusion criteria
- randomization

Assignment of individual patient identification code (IPIC)

The Investigator must ensure the anonymity of the trial subjects. The full names of all patients participated in the trial are strictly confidential.

After signing the Informed Consent Form, each patient will be assigned an Individual Patient Identification Code (IPIC) in accordance with the current legislation (Table 6).

Table 6. Individual Patient Identification Code

Permission of the Ministry of Health of the Russian Federation No.	Permission's date of issue, DD/MM/YYYY/	Serial number of the medical organization specified in the Permission	Patient's initials	Patient's date of birth, DD/MM/YYYY/	A unique number assigned to the patient by the Investigator, consisting of letters and numbers (the name of the protocol and the screening number under which the patient was included in the trial)
--	---	---	--------------------	--------------------------------------	--

The individual patient identification code (IPIC) is established by the Insurant based on the patient data provided by the Investigator. The individual patient identification code is reported by the Insurant to the Investigator for inclusion in his medical documentation. The IPIC will be reflected in the primary documentation, Case Report Form, and Patient Information Sheet with the informed consent form. The IPIC will be transmitted by the Code Registry by the Insurant to the Insurer.

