The individual identification code assigned to the patient is not subject to change.

The Investigator should maintain a separate Identification Registry containing the individual numbers, surnames, dates of birth, addresses, phone numbers, and medical records (if available). Only the initials, dates of birth, and unique patient numbers that are part of the Individual Patient Identification Code will be used in the report and trial documentation.

The randomization plan will be known by the Principal Investigator and Regulatory Authorities.

Visit 2.

- Administration of Fortelyzin® or Actilyse®.
- On Visit 2, the changes in neurological status will be recorded, as well as registration and evaluation of bleeding and adverse events based on patient complaints, data from neurological, physical, and laboratory-instrumental studies.

Table 7. Monitoring of parameters at the moment of thrombolysis

Trial parameter	Frequency of examination
BP	Every 15 minutes to 2 hours after the start of thrombolysis
Vital signs	Every 30 minutes for 6 hours
NIHSS	Every 15 minutes for 1 hour
Meningeal symptoms	Every 15 minutes for 1 hour

Table 8. Monitoring of parameters during the first day (24h) after thrombolysis

Trial parameter	Frequency of examination
BP	Every hour until the end of the day (within 24 hours)
Vital signs	Every 30 minutes to 6 hours, then every hour until the end of the day
Meningeal symptoms	Every hour for 24 hours
NIHSS	Every hour for 24 hours

- CT/MRI 24 hours after TLT or if the patient's condition worsens
- assessment of CT changes according to ASPECTS
- registration of adverse events (AE)
- assessment of bleeding

All adverse events identified should be recorded in the Case Report Form (CRF). The Investigator should report the adverse events to Roszdravnadzor within the next 24 hours. The assessment of bleeding is carried out according to the corresponding scales (see Safety assessment). Monitoring of coagulogram parameters (fibrinogen) will be carried out within 24 h from the time of Fortelyzin® or Actilyse®

administration. CT/MRI examination of the brain will be repeated 24 hours after the thrombolysis or if the patient's condition worsens.

During the visit, patients will receive treatment in accordance with the Russian Clinical Guidelines for Thrombolytic Therapy in Ischemic Stroke, 2015.

Visit 3.

- verification of the stroke subtype according to TOAST criteria
- measurement of vital signs
- physical examination

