- during the infusion of the main dose, it is allowed to stop and continue the administration of Actilyse®, but the total duration of drug administration cannot exceed one hour after bolus (10% of the dose).
- Labeling: «Product for clinical trial only».

Previous treatment

Every effort should be made to find out what treatment the patient received within 30 days before administration of the study drug. The names of the drugs, the start and end dates of their use should be registered in the CRF.

Permitted concomitant therapy

In the first 24 hours after thrombolysis, the use of drugs to lower blood pressure is allowed: angiotensin-converting enzyme inhibitors and angiotensin receptor antagonists. If blood pressure drops during thrombolysis, the use of vasopressors (dobutamine, dopamine, and norepinephrine) is allowed.

In the case of allergic reactions during thrombolysis, the use of glucocorticoids and antihistamines is allowed.

If severe bleeding (especially from non-compressible vessels) occurs, the thrombolytic should be stopped and administration of fresh frozen plasma or fresh blood should be performed.

After 24 hours after thrombolysis, the use of antiplatelet agents – ASA, clopidogrel, ticlopidine, ticagrelor, anticoagulants: unfractionated or low-molecular-weight heparin, warfarin, dabigatran, bivalirudin, apixaban, rivaroxaban, fondaparinux is allowed. These drugs are permitted after thrombolysis only after CT/MRI examination to exclude intracranial hemorrhages (symptomatic and asymptomatic) and hematomas (Clinical recommendations for thrombolytic therapy in ischemic stroke, 2015).

In the absence of hemorrhagic transformation, the use of ASA is allowed during the entire follow-up period (90 days) after thrombolysis.

Prohibited concomitant therapy

In this trial, the use of antiplatelet agents (ASA, clopidogrel, ticagrelor, ticlopidine), anticoagulants (NPH, NMG, fondaparinux), oral anticoagulants (phenylin, syncumar), vitamin K inhibitor (warfarin), direct inhibitors of thrombin and blood clotting Factor X (dabigatran, bivalirudin, apixaban, rivaroxaban), glycoprotein IIb/IIIa receptor blockers, drugs that affect the rheological properties of blood (agapurin, vincocetine) is prohibited within 24 hours after thrombolysis.

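### Entry rule and drug contraindication disagree on diastolic pressure: patients are excluded above 110 mm Hg, but Fortelyzin is contraindicated above 105. One figure must be wrong, and the protocol does not show which.

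*Combined protocol and SAP*

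**What the plan says.** Blood pressure limits for treating stroke patients appear in three places.

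- **Section 7.2 and the exclusion criteria in the protocol summary** use the same words: "Systolic blood pressure greater than 185 mm Hg or diastolic blood pressure greater than 110 mm Hg". Both also exclude patients who need intravenous drugs to get down to those limits.
- **Section 2, Contraindications, item 14**: "Arterial hypertension greater than 185/105 mm Hg or the need for intensive reduction below these figures". This list follows directly on the stroke indication, "Ischemic stroke in men and women aged 18 and older", so it does not belong to the myocardial infarction use described earlier in that section.

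Two other places bear on how the limits are used. Section 3, on bleeding risk, states that "a clear selection of patients taking into account all contraindications allows, in most cases, to minimize the risk of bleeding". Section 9, Visit 1, requires an assessment of "compliance with the inclusion/exclusion criteria" and then randomizes.

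**The concern.** An entry rule may be stricter than the drug information without harm. Here it is looser, on a safety threshold for a thrombolytic whose main stated risk is bleeding.

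If 105 is the true limit for Fortelyzin, a site that follows Section 7.2 to the letter can give the study drug to a patient for whom the protocol contraindicates it. If 110 is the true limit, Section 2 gives investigators a wrong contraindication, and a careful investigator may turn away an eligible patient. Either way, staff treating within 4.5 hours of onset should not have to choose between two figures.

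**Working it through.** The plan has no calculated figure to reproduce on this point. The check sets the limits side by side.

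| Place | Systolic limit (mm Hg) | Diastolic limit (mm Hg) |
|---|---|---|
| Section 7.2 | 185 | 110 |
| Protocol summary | 185 | 110 |
| Section 2, item 14 | 185 | 105 |

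**Size of the gap.** 110 − 105 = 5 mm Hg. The whole-number diastolic readings that pass Section 7.2 but exceed item 14 are 106, 107, 108, 109 and 110.

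**Example.** Take a patient at 180/108 mm Hg who needs no intravenous drugs to stay within 185/110 and meets every other criterion.
- Section 7.2: 180 ≤ 185 and 108 ≤ 110, so not excluded.
- Item 14: 108 > 105, so contraindicated.

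**How item 14 is read.** The example takes 185/105 to be exceeded when either component is exceeded. Item 14 does not say so in words, whereas Section 7.2 joins its two limits with an explicit *or*. If both components had to be exceeded, every patient meeting item 14 would have a systolic pressure above 185 and would already be excluded by Section 7.2, so there would be no gap. On that reading, though, a patient at 180/120 would fall outside the contraindication, which is hard to believe was meant. The either-component reading is the natural one.

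**Does another entry step catch the patient?**
1. Section 7.2 has 30 exclusion criteria. One sets a blood pressure limit. None excludes patients with a Fortelyzin contraindication in general; even the hypersensitivity criterion names only the comparator and a residue of its manufacture ("Increased sensitivity to alteplase, gentamicin (residual traces from the production process").
2. Visit 1 checks the inclusion and exclusion criteria. Visit 2 opens with drug administration and lists no contraindication check.
3. Section 3 connects patient selection with the contraindications, but as a description of how bleeding risk is reduced. It does not amend Section 7.2, and it points to the list that disagrees with Section 7.2.
4. Later safeguards start too late to settle eligibility. Table 7 has blood pressure measured "Every 15 minutes to 2 hours after the start of thrombolysis", and Section 10 states: "In the first 24 hours after thrombolysis, the use of drugs to lower blood pressure is allowed".

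**The case against.** The best counter-argument is that sites face little practical doubt. Section 7.2 and the summary agree, and Visit 1 applies those criteria. Section 2 is general drug information and not a copy of the eligibility list. It differs elsewhere too: it allows use with caution after age 80 where Section 7.1 stops at 80, and it sets a 10-day window for puncture of non-compressible vessels where the apparently corresponding criterion in Section 7.2 sets 7 days. An investigator who reads Section 3 would also consult the contraindications.

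Much of this stands. Sites would probably apply 110, and Section 3 means that the contraindications are not wholly disconnected from selection. But it does not remove the conflict. Section 2 cannot be dismissed as background: item 21 of the same list contains an instruction for this study, a urine pregnancy test beforehand. The age difference is in the cautious direction; the diastolic difference is not. Section 3 leaves a reader with two limits and no order of precedence.

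A reader might infer that Section 7.2 is the faulty text, or that contraindicated patients will in fact be dosed. The documents support neither. The figure 110 appears twice and 105 once, which settles nothing about which is right, and the dosing consequence follows only if 105 is correct.

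**Conclusion.** The contradiction is in the current text and holds. The same stroke patients are subject to two diastolic limits 5 mm Hg apart, with the rule that governs entry looser than the stated contraindication. What is shown is that one figure must be wrong, not which one.

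This rests on reading item 14 as breached when either component is exceeded, and on Section 7.2 being the operative entry rule. The affected band is diastolic 106 to 110 mm Hg with systolic at or below 185, in patients not needing intravenous drugs to reach 185/110. How many patients fall there cannot be estimated from the documents.

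Severity is minor. The sample size in Section 17 uses a 54.8% response in both groups, a 16% margin and 80% power. None of these depends on the diastolic limit, and the primary analysis is likewise unaffected.

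**What to change.** The sponsor should confirm the correct diastolic limit for Fortelyzin and make the three places agree.

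- **If 105 is correct:** change the diastolic exclusion in Section 7.2 and in the summary to above 105 mm Hg, keeping the clause on intravenous drugs. Eligibility is decided before randomization, so the limit would apply to all randomized patients, including those allocated to Actilyse. The cost is two edits and the loss, from both arms, of an unknown number of patients at 106 to 110 mm Hg.
- **If 110 is correct:** leave Section 7.2 and the summary alone and change item 14 to 185/110 mm Hg. The cost is one edit.

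Until the sponsor answers, sites should work to the stricter 105. Neither route requires a change to the statistical plan.

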2. GENERAL INFORMATION ABOUT THE STUDY DRUG

Brand name: Fortelyzin®, valid registration number - 001941 as of December 18, 2012.

Chemical name: recombinant protein, which contains the amino acid sequence of staphylokinase.

Pharmacology and pharmacokinetics

Fortelyzin® refers to the so-called group of fibrin-selective thrombolytics.

The active substance of Fortelyzin® is Forteplase, which is a single-chain molecule consisting of 138 amino acids with a molecular weight of 15.5 kDa.

Forteplase® is an original recombinant protein obtained using genetically engineered *E. coli* and containing the amino acid sequence of modified (non-immunogenic) staphylokinase.

In contrast to the native staphylokinase, 3 amino acids in the immunodominant epitope were replaced in the Forteplase® molecule.

Forteplase® is not an enzyme and activates plasminogen forming a stoichiometric complex at a 1:1 ratio.

Lysine-11 of the N-terminal site of plasminogen and glutamine-46, lysine-50, glutamine-65, and asparagine-69 of the C-terminal site of the drug play a key role in the interaction of Forteplase® and plasminogen.

Along with this, the N-end of the substance acts as a "moving arm" that captures the plasmin molecule and, as a result, a ternary complex composed of plasminogen-Forteplase®-plasmin, is formed.

Depending on different conditions, plasminogen can take three different conformations: α , β , and γ .

Plasminogen was determined to have a closed α -conformation in the bloodstream; a semi-open β -conformation occurs when plasminogen is bound to intact fibrin and a fully open γ -conformation occurs when plasminogen is bound to partially degraded fibrin.

The conversion of plasminogen to plasmin by plasminogen activators requires an open γ -conformation. Forteplase® interacts only with plasminogen in the γ -

conformation and does not bind to plasminogen in the closed form, i.e., which is in the circulation.

The mechanism of Forteplase® fibrinolytic action involves its initial binding to plasmin generated on the fibrin clot with subsequent activation of γ -plasminogen. Fortelyzin®, compared to the classic plasminogen activator Actilyse®, is the only thrombolytic that forms a ternary complex: plasmin-Forteplase-plasminogen activator.

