- The number of platelets is less than 100,000/ μ L.
- Blood glucose less than 2.8 mmol/l or more than 22,5 mmol/l.
- Hemorrhagic diathesis, including renal and hepatic insufficiency.
- Data on bleeding or acute trauma at the time of examination.
- Seizures in the onset of the disease, if there is no certainty that the seizure is a clinical manifestation of ischemic stroke with a postictal residual deficiency.

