10. THERAPY DURING THE TRIAL

Study drug: Fortelyzin®

Manufacturer: Supergene, LLC, Russia

Drug description

Pharmaceutical form: lyophilizate for preparation of a solution for intravenous administration, supplied with a solvent

Detailed description:

Lyophilizate: tablet-like freeze-dried mass of white or almost white color.

Solvent: colorless transparent liquid.

Reconstituted solution: colorless, transparent or slightly opalescent liquid.

Composition:

Active substance: Forteplase® (recombinant protein containing the amino acid sequence of staphylokinase) 5 mg (745,000 IU).

Excipients: L-arginine - 15,0 mg, L-histidine - 2,0 mg, glycine - 30,0 mg, povidone - 17:20,0 mg, polysorbate -20:0,4 mg.

Solvent: 5mL ampule of sodium chloride 0.9% solution for injection

Dosage regimen: Fortelyzin® will be assigned at a dose of 10 mg (1,490,000 IU).

Route of administration: intravenously in the form of a single bolus injection for 5-10 sec. The solution of Fortelyzin® is prepared immediately before administration: the content of a 5 mg vial (745,000 IU) is diluted in 5 ml of 0.9% sodium chloride solution. Non-storable!

Labeling: «Product for clinical trial only».

Active Comparator: Actilyse®

Manufacturer: Boehringer Ingelheim Pharma GmbH & Co. KG

Drug description

Pharmaceutical form: lyophilizate for preparation of a solution for infusion supplied with a solvent.

Detailed description:

Lyophilizate: freeze-dried mass of white or light yellow color.

Solvent: colorless transparent liquid

Composition:

Active substance: Alteplase 50,0 mg

Excipients: L-arginine: 1742.0 mg,

Phosphoric acid, 85 %: up to pH 7.2 ± 0.2,

Polysorbate 80: 3.5-5.0 mg.

Note

The excess is 3.5 % of the nominal amount of the active ingredient and excipients in the vial.

Residual traces: gentamicin (used in the production process).

Each vial of solvent contains:

Water for injection: 50 ml

1 ml of the solution after dilution contains 1 mg of alteplase.

Dosage regimen:

Actilyse ® is administered in accordance with the instructions for use in ischemic stroke at a dose of 0.9 mg/kg, maximum 90 mg, if a patient's weight exceeds 55 kg:

- 10% of the dose is administered intravenously via a syringe for one minute (bolus);
- the main dose of the drug (90% of the dose) is administered within 60 minutes (using a syringe dispenser / infusomat);

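### Section 7.2 and the synopsis let in patients with brief, non-traumatic resuscitation in the past 10 days, whom Section 2, item 20 lists as contraindicated for Fortelyzin

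*Combined protocol and SAP*

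**What the plan says.** Section 2 sets out an indication for Fortelyzin, "Ischemic stroke in men and women aged 18 and older", followed by a numbered list of contraindications. Item 20 reads "Extensive surgery, trauma, delivery, puncture of non-compressible vessels, cardiopulmonary resuscitation within the last 10 days". It puts no minimum length on the resuscitation and does not require it to have been traumatic.

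Section 7.2 splits the same events into separate bullets. The one on resuscitation is "Prolonged or traumatic cardiopulmonary resuscitation (more than 2 min"), with no look-back period. The synopsis has the same wording. Three other bullets in 7.2 come near the topic:

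- "Data on bleeding or acute trauma at the time of examination"
- "minor surgery or invasive manipulation in the last 10 days"
- "Puncture of uncompensated arteries and veins during the last 7 days"

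In Section 9, the Visit 1 steps name the inclusion/exclusion criteria as the eligibility check. They do not mention the Section 2 list. Section 3 remarks in general terms that careful selection with regard to contraindications keeps bleeding risk down.

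**The concern.** A trial's exclusion list would normally be at least as strict as the contraindications that the same protocol gives for the study drug in the trial's indication. Here, for one type of patient, it is looser, and no reason is given.

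The stake is bleeding safety. Fortelyzin is given as a single bolus over 5 to 10 seconds, so the Section 2 advice to stop administration if life-threatening bleeding occurs has little use once the dose is in. Selection before dosing is the main control, and sites apply it against a 4.5-hour limit.

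**Working it through.** No power, margin or sample size figure is involved. The check sets each component of Section 2, item 20 beside the Section 7.2 bullets.

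| Component | Section 2, item 20 | Section 7.2 | Result |
|---|---|---|---|
| Major surgery | 10 days | 14 days | Covered |
| Trauma | 10 days, no grade clearly stated | Severe injuries, 14 days; acute trauma at examination | Time window covered; grade cannot be settled |
| Delivery | 10 days | 10 days | Covered |
| Puncture of non-compressible vessels | 10 days | 7 days, with an adjacent 10-day bullet on invasive manipulation | Gap of 0 to 3 days |
| Resuscitation | Any, 10 days | Only if prolonged (more than 2 min) or traumatic, no time limit | Brief, non-traumatic cases not covered |

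**Resuscitation.** The 7.2 bullet is wider than item 20 in time and narrower in type. Prolonged or traumatic resuscitation is excluded whenever it took place. Resuscitation of 2 minutes or less, without trauma, is not excluded on any of the 10 days. The other bullets do not close this. The one on acute trauma does not reach a non-traumatic event, and brief resuscitation is not in itself surgery or an invasive manipulation. No criterion says that a Section 2 contraindication also excludes the patient.

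This takes the reading of 7.2 more favourable to the plan, in which the 2-minute limit qualifies only *prolonged*. If it also qualifies *traumatic*, brief traumatic resuscitation escapes that bullet as well.

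**Puncture.** On the puncture bullet alone the shortfall is 10 - 7 = 3 days (days 8, 9 and 10). If the puncture counts as an invasive manipulation, it is 10 - 10 = 0 days. The comparison also assumes that *uncompensated* in 7.2 is a translation of *non-compressible*.

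**Scale.** Item 20 concerns Fortelyzin, so it bears on the 168 of 336 patients allocated to that drug. The documents give no frequency of recent brief resuscitation, so no expected count can be calculated.

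**The case against.** The strongest reply is that Section 2 is background, headed "GENERAL INFORMATION ABOUT THE STUDY DRUG", and that 7.2 is a separate and more specific list that was never meant to copy it. Section 7.2 is stricter in places: 14 days rather than 10 for major surgery, no time limit on prolonged or traumatic resuscitation, and an upper age of 80 where Section 2 advises only caution above that age. The 2-minute threshold could then be a deliberate clinical choice, and editing item 20 would remove the mismatch just as well.

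Part of this stands. The documents do not show which rule is clinically right. But they give no rationale for admitting patients whom the protocol's own drug information lists as contraindicated, and tightening 7.2 is the cautious way to resolve it.

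Four stronger readings are tempting, and the documents do not support them:

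- *Sites are given two conflicting eligibility instructions.* Visit 1 points only to the inclusion/exclusion criteria. The Section 3 remark is risk narrative and sets no second test. A site that follows Visit 1 gets one answer, from 7.2.
- *There is a real 3-day hole for vessel punctures.* Exclusions are cumulative, and the 10-day bullet on invasive manipulation probably catches most of these cases. What is left is mainly unclear wording.
- *The same patient is contraindicated for Actilyse.* The protocol says only that it "is administered in accordance with the instructions for use in ischemic stroke", and those instructions are not reproduced.
- *Ungraded trauma in item 20 goes beyond the severe injuries in 7.2.* The text does not settle this, because *extensive* at the head of item 20 may or may not carry over to trauma.

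**Conclusion.** The point holds for resuscitation. A patient with brief, non-traumatic resuscitation in the past 10 days is contraindicated for Fortelyzin under Section 2 and can be randomised under Section 7.2 and the synopsis. It is an inconsistency between the drug information and the operative criteria, on a safety matter, and of the lowest severity.

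The number of patients is likely to be very small, since such a patient must also have a qualifying stroke treated within 4.5 hours and meet no other exclusion. A reader might infer a threat to the comparison. There is none: the rule acts before randomisation and is the same in both arms.

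The conclusion assumes that the 10-day window in item 20 applies to resuscitation, as its position in the sentence indicates, and that *extensive* does not qualify resuscitation. Carrying that adjective through the whole list would not fit delivery or vessel puncture. Confidence is moderate.

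**What to change.** In Section 7.2 and the synopsis, reword the resuscitation bullet to: *Cardiopulmonary resuscitation that was prolonged (more than 2 min) or traumatic, or any cardiopulmonary resuscitation in the preceding 10 days.* This keeps the present exclusion and adds the missing case. If the sponsor holds that brief resuscitation is acceptable, it should say why and amend item 20 instead.

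As a wording point in the same amendment, the puncture bullet can be set to 10 days and to *non-compressible* vessels, which also brings it into line with its neighbour. A single line-by-line check of the Section 2 contraindications against 7.2 would be sensible at that time.

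The cost is two bullets in two places, 2 × 2 = 4 edits, and possibly a few fewer eligible patients. The planned 336 patients, the power and the analysis do not change.
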